4.1 OBJECTIVES, SPECIFIC AIMS & RATIONALE

The objective of this sub-study is to determine the extent of variation in use of Advice and Guidance (A&G) in primary care. The specific aims are to determine:

1) if use of A&G has increased over time in comparison to direct referrals

NIHR 158681BADGER			
Protocol Version 2.0 18/06/2024	CPMS: 58336	IRAS No: 333799	CPRD ID: 24_004022

- 2) variation in use of A&G by socio-demographic characteristics
- 3) which specialties and health conditions have higher rates of A&G
- 4) the percentage of A&G which end up with a direct referral.

This study is the first part of a programme of work which has the overall aim to understand whether A&G reduces waiting times and access to specialist care as planned, without making the quality of patient care worse. This initial study will examine changes in use of A&G over time and how it varies by sociodemographic characteristics and specialty.

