4.2.8 Exposures, outcomes and covariates

1) Advice & Guidance

We will determine coded A&G events and, where possible, the specialty linked to the A&G. When a Choose and Book referral is made through e-RS (by selecting either the satellite button for "advice and guidance" which equates to an A&G request or the "Refer/Advice" satellite button which equates to the standard or direct referral to secondary care), the referral must be saved before the activity can be completed and exited back to the clinical software system. To save the activity, a code must be entered to then move back into another part of the healthcare record. For A&G requests, the coded term is "Advice and guidance requested." We will also include in our codelist the code "Advice and guidance received" which we will use to indicate A&G if the patient does not have an "Advice and guidance requested" code within the same study time period. We will map A&G to specialty (e.g. rheumatology, neurology) and type of health condition (e.g. musculoskeletal, cardiovascular). Given A&G coded events may not routinely have the specialty recorded we will use information from direct referrals (sampled from 3 specified years - 2015, 2019, 2023 - within our study period) as the basis for mapping to specialty. We will first determine morbidity/symptom codes recorded on the date of all direct referrals (defined below) with a named specialty, or in the prior 2 weeks. We will determine which Read or SNOMED CT codes are most frequently recorded with referral to each specialty and use these to map (impute) specialties in those with an A&G event based on matching these codes to Read/SNOMED CT morbidity or symptom codes recorded on the date of A&G or in the prior 2 weeks. Where the specialty is still unknown after this mapping exercise, we will review all codes in the 2 weeks prior to or on date of A&G request and agree on specialty (guided by Read code chapter) by consensus or define as unknown if no consensus. Type of health condition will be based on specialty or morbidity/symptom code at date of A&G event.

2) Direct referral

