To derive the comparative prevalence and incidence of elective referrals, direct routine referrals will be determined using codes with a term indicating a referral and defined by consensus of study team to indicate a routine referral to a specialty (i.e. not fast track or referral with an intention to admit / emergency referral). To ascertain A&G events which result in a direct referral, we will determine

NIHR 158681BADGER			
Protocol Version 2.0 18/06/2024	CPMS: 58336	IRAS No: 333799	CPRD ID: 24_004022

referrals within 122 days (4 months) after date of an A&G request. These will be defined as i) a direct referral code defined as above and by ii) linking events in the Referrals table to the Observation table and determining duration of time between the linked observation event and the A&G request date. We will also determine referrals within 122 days (4 months) before an A&G request to see how often A&G requests follow a referral request. As a sensitivity analysis we will repeat for 365 days (12 months) either side of the A&G request date. Code lists for A&G have been derived and used in our CPRD feasibility study (FS_002830). The draft code list for direct referral has also been developed. These code lists are included in the appendix.

Covariates:

- 1) Age at date of A&G request (categorised)
- 2) Sex
- 3) Geographical region
- 4) CCG pseudonym
- 5) Ethnicity group
- 6) Deprivation (based on IMD quintiles)

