4.3 DATA / STATISTICAL ANALYSIS

We will determine the annual total number of A&G and total number of routine direct referrals from 2015 to 2023. Annual prevalence will then be defined as the total number of patients with i) an A&G and ii) a routine referral code recorded within each calendar year, divided by the total registered population at the start of each calendar year and expressed per 100,000 persons. Annual incidence will be defined (as in our previous incidence studies) as the total number of patients with i) A&G and ii) routine referral codes recorded within each calendar year who have no recorded A&G or routine referral codes in the previous 24 months, divided by the total registered population with at least 24 months registration at the start of each calendar year, and expressed per 100,000 persons. We will determine prevalence and incidence overall, and stratified by age and sex.

Patterns of A&G use (number, prevalence, incidence) will also be described across specialties and type of health condition, and by neighbourhood deprivation, ethnicity, CCG, and geographical region to assess if any change over time in consultation incidence and prevalence varies by these characteristics. We will produce caterpillar plots to show variation by geographical region and CCG. We will repeat for quarterly incidence and prevalence of A&G (up to date of most recent CPRD Aurum build). We will use joinpoint regression analysis and segmented regression on the annual and quarterly prevalence and incidence to determine impact of the COVID pandemic [2020/2021] and changes in policy on A&G.

Within those with A&G we will derive the percentage with a recorded referral in the 122 days (4 months) i) before and ii) after A&G record and compare these over time, and by the covariates (excluding those with less than four months of follow-up), descriptively and by using binary logistic regression. We will repeat for the sensitivity analysis of 12 months. We will descriptively compare trends in incidence and prevalence of A&G and routine direct referrals with publicly available data on trends on e-referrals from https://digital.nhs.uk/dashboards/ers-open-data which currently covers the period October 2019 to March 2024.

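### WP1a aim 4 counts a recorded referral to any specialty as the outcome of an A&G, so unrelated referrals push the percentage up and can distort the group comparisons

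*Protocol*

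**What the plan says.** Section 4.1 lists as the fourth aim of WP1a "the percentage of A&G which end up with a direct referral". Section 4.2.8 (direct referral) words the outcome as a consequence: "To ascertain A&G events which result in a direct referral, we will determine" "referrals within 122 days (4 months) after date of an A&G request".

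Two routes then define a referral:
- Route (i) is a code "defined by consensus of study team to indicate a routine referral to a specialty".
- Route (ii) is a Referrals-table event joined to the Observation table, and what is taken from the join is "determining duration of time between the linked observation event and the A&G request date".

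Neither route refers to the specialty or condition of the A&G. Route (ii) states no restriction to routine referrals, and how the two routes combine is not clear.

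The same rule is used for the 122 days before the request. For both directions the plan adds: "As a sensitivity analysis we will repeat for 365 days (12 months) either side of the A&G request date".

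Section 4.3 makes this the analysis variable: "we will derive the percentage with a recorded referral in the 122 days (4 months) i) before and ii) after A&G record". It is to be compared over time and by the covariates, descriptively and by logistic regression.

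Section 4.2.8 also maps A&G events to a specialty and a type of health condition, partly by using direct referrals that name a specialty. That mapping is not used to link a referral to the A&G. Section 4.3.3 expects any misclassification to be random and to cause no significant bias.

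**The concern.** The aim is about referrals that follow from the A&G. The measure is whether the patient has a recorded referral near it in time. A dermatology A&G followed three months later by an unrelated orthopaedic referral counts as converted. This error runs in one direction only, so it is not random misclassification.

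The comparisons are most exposed. People who are referred often for other problems will have more coincidental referrals in the window. If that background rate differs by age, deprivation, ethnicity, CCG or calendar year, the percentage will differ even where conversion does not. Section 4.2.6 says any inequity found will feed into recommendations, and Section 10.1.2 plans a WP1a report to policy makers and commissioners by month 12. A difference in general referral demand could then be read as a difference in how A&G works.

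**Working it through.** **The plan's own precision (Section 4.2.5).** Half-width = 1.96 × √(p(1−p)/n) with p = 0.5.
- n = 108,000: 1.96 × √(0.25/108,000) = 0.298 points. The plan states ±0.3.
- n = 1,080 (a 1% category): 2.98 points. The plan states ±3.

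Both figures reproduce and are not in dispute.

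**Inflation model.** Let c be true conversion and λ the rate of unrelated recorded referrals per person-year among A&G patients. λ is not in the protocol and every value below is an assumption. If unrelated referrals occur at a constant rate, independently of conversion:
- chance of at least one in t days: b = 1 − exp(−λt/365)
- observed percentage = c + (1 − c)b

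With c = 40%, held the same for both windows:

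| λ per person-year | b, 122 days | observed, 122 days | b, 365 days | observed, 365 days |
|---|---|---|---|---|
| 0.2 | 6.5% | 43.9% | 18.1% | 50.9% |
| 0.4 | 12.5% | 47.5% | 33.0% | 59.8% |

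**Sensitivity to λ.** Inflation at c = 50%, in points:

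| λ per person-year | 122 days | 365 days |
|---|---|---|
| 0.05 | 0.8 | 2.4 |
| 0.1 | 1.6 | 4.8 |
| 0.2 | 3.2 | 9.1 |
| 0.5 | 7.7 | 19.7 |
| 1.0 | 14.2 | 31.6 |

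**Rate that equals the stated half-width.** At c = 50%, 0.3 points needs b = 0.003/0.5 = 0.006. Then λ = −ln(1 − 0.006) × 365/122 ≈ 0.018 per person-year.

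**Two groups with equal conversion.** At c = 40%, rates of 0.2 and 0.4 give 43.9% and 47.5% at 122 days. That is a gap of 3.6 points and an odds ratio of (0.475/0.525)/(0.439/0.561) ≈ 1.16, with no difference in conversion.

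**Effect of matching on specialty.** Assume that 5% to 20% of unrelated referrals happen to fall in the A&G's own specialty (also not in the protocol). At c = 50% and λ = 0.2, inflation falls from 3.2 to 0.2–0.7 points at 122 days, and from 9.1 to 0.5–2.0 points at 365 days.

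**The case against.** WP1a is declared descriptive and hypothesis generating, and this percentage is one of four descriptive aims. Section 4.3 describes it neutrally as a recorded referral in a window. Section 4.3.1 admits possible confounding of referral following an A&G, and Section 4.3.3 disclaims causal conclusions. These points lower the severity. They do not remove the mismatch, because a descriptive percentage must still measure what its aim names, and the limitations sections do not mention unrelated referrals.

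Specialty matching is also imperfect. Section 4.2.8 says A&G events may not routinely carry a specialty, so it will often be imputed from nearby codes, and sometimes left unknown. Some direct referrals may not name one either. The audit cited in Section 1.1.2 had 8% of requests ending in referral to a different specialty. Making a match the only definition of conversion would create false negatives that depend on coding. This stands, and it is why the matched figure should sit beside the existing one and not replace it.

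Four stronger readings are tempting, and the documents do not support them:
- **That aim 4 will be overstated by a known amount, or overstated on balance.** No background rate is given. Section 4.3.2 treats an uncoded referral as no referral, which biases downward.
- **That a rise from 122 to 365 days would be mainly background.** The table shows this only because c is held at 40% in both windows, which builds in no late conversion.
- **That inflation is always greatest in people referred often.** It equals (1 − c)b. At 122 days, λ = 0.5 with c = 90% gives 1.5 points, while λ = 0.1 with c = 30% gives 2.3. The statement holds at equal conversion.
- **That the error dwarfs the stated precision throughout.** Against ±3 points in a 1% category, an inflation of 3.9 to 7.5 points is 1.3 to 2.5 times.

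**Conclusion.** The measure does not isolate what aim 4 asks for. Any non-zero rate of unrelated referral raises it, and at equal true conversion it rises more where background referral is more frequent. The planned comparisons can therefore show differences that are not differences in conversion, and the 365-day analysis is no check on this.

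The direction of this one component is certain; its size is not. Under an assumed 0.2 to 0.4 unrelated referrals per person-year it is 3.9 to 7.5 points at 122 days for true conversion of 40%, and about 0.018 per person-year already adds 0.3 points at 50%. These figures rest on assumed rates and on constant, independent background referral. They are illustrations, not estimates, and they say nothing about the net bias after under-recording. The point is one that should be fixed before WP1a is analysed; it does not invalidate the work package.

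**What to change.** - **Label.** Call the existing measure *any routine referral within 122 days of A&G*, and say how routes (i) and (ii) combine and whether route (ii) is limited to routine referrals.
- **Add a matched measure.** Beside it, overall and in every covariate and time comparison, report the percentage with a referral matching the A&G's specialty (or condition), using the Section 4.2.8 mapping. Show A&Gs or referrals of unknown specialty separately.
- **Interpretation.** Present the matched figure as approximately a lower bound, since redirected referrals and mapping errors are missed. Present the any-referral figure as approximately an upper bound for recorded referrals.
- **Other windows.** Treat the before window and the 365-day repeat in the same way.
- **Limitations.** Amend Section 4.3.3 so that this misclassification is not described as random.
- **Optional.** A background correction, c = (observed − b)/(1 − b), with b taken from an earlier control window of equal length in the same patients. It is approximate, because it assumes the same referral rate before and after the episode. It should be limited to patients with enough look-back: Section 4.2.7 requires 24 months of registration only for incident A&G (unless aged 2 years or under), and recorded events start in January 2015.

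The cost is some extra programming on data already planned for extraction, and mapping error in the matched figure.

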4.3 DATA / STATISTICAL ANALYSIS

We will determine the annual total number of A&G and total number of routine direct referrals from 2015 to 2023. Annual prevalence will then be defined as the total number of patients with i) an A&G and ii) a routine referral code recorded within each calendar year, divided by the total registered population at the start of each calendar year and expressed per 100,000 persons. Annual incidence will be defined (as in our previous incidence studies) as the total number of patients with i) A&G and ii) routine referral codes recorded within each calendar year who have no recorded A&G or routine referral codes in the previous 24 months, divided by the total registered population with at least 24 months registration at the start of each calendar year, and expressed per 100,000 persons. We will determine prevalence and incidence overall, and stratified by age and sex.

Patterns of A&G use (number, prevalence, incidence) will also be described across specialties and type of health condition, and by neighbourhood deprivation, ethnicity, CCG, and geographical region to assess if any change over time in consultation incidence and prevalence varies by these characteristics. We will produce caterpillar plots to show variation by geographical region and CCG. We will repeat for quarterly incidence and prevalence of A&G (up to date of most recent CPRD Aurum build). We will use joinpoint regression analysis and segmented regression on the annual and quarterly prevalence and incidence to determine impact of the COVID pandemic [2020/2021] and changes in policy on A&G.

Within those with A&G we will derive the percentage with a recorded referral in the 122 days (4 months) i) before and ii) after A&G record and compare these over time, and by the covariates (excluding those with less than four months of follow-up), descriptively and by using binary logistic regression. We will repeat for the sensitivity analysis of 12 months. We will descriptively compare trends in incidence and prevalence of A&G and routine direct referrals with publicly available data on trends on e-referrals from https://digital.nhs.uk/dashboards/ers-open-data which currently covers the period October 2019 to March 2024.

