5.2.7 Definition of the study population

All individuals in the CPRD Aurum database, regardless of age, with a first recorded index tracer condition between 01/01/2015 to 31/12/2022 and 24 months prior registration in CPRD Aurum. We will compare outcomes for patients with a recent history of A&G to those with direct referral, stratified by tracer condition. A&G and direct referrals will be obtained from primary care records in the 24 months prior to index (first diagnosis) date. Patients with both A&G and direct referral will be classified based on whichever happened first. We will include age at index date, gender, neighbourhood deprivation, geographical region, and ethnicity, as common covariates for all analyses as well as covariates (e.g. multiple long term conditions) specific to each tracer condition. There is no comparison or control group.

The tracer conditions will be informed from the work in WP1, including interviews with PCCs, and the experiences and advice of our PPIE and Stakeholder groups.

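### Work package 1a counts referrals that follow an A&G in its direct-referral totals and prevalence, so any move from direct referral to A&G will look smaller than it is

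*Protocol*

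**What the plan says.** Section 4.1 sets as its first aim to determine "if use of A&G has increased over time in comparison to direct referrals", and as its fourth to determine "the percentage of A&G which end up with a direct referral".

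Section 4.2.8 defines the comparator: "direct routine referrals will be determined using codes with a term indicating a referral and defined by consensus of study team". Only fast-track and emergency or admission referrals are left out. For the fourth aim, the same section looks for "referrals within 122 days (4 months) after date of an A&G request" and finds them in two ways. The first is "a direct referral code defined as above"; the second links the Referrals table to the Observation table.

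Section 4.3 then fixes the measures: "We will determine the annual total number of A&G and total number of routine direct referrals from 2015 to 2023". Annual prevalence is the number of patients with each kind of code in the year over the registered population. Neither measure is split by whether an A&G came first. Incidence additionally requires 24 months free of A&G or routine referral codes. Separately, among patients with A&G, the percentage with a referral in the 122 days before and after is compared over time, with 365 days as a sensitivity analysis.

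Work package 2 separates the pathways. Section 5.2.7 states: "Patients with both A&G and direct referral will be classified based on whichever happened first". Section 5.3 uses four groups for the utilisation outcomes: A&G only, direct referral only, both, neither.

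**The concern.** The first aim sets A&G beside direct referral over time. A referral that results from an A&G is found through the same codes that make up the direct-referral series, so it lies inside the comparator. As A&G grows, the referrals it generates replace part of whatever is lost from referrals made without it.

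A fairly stable referral series beside rising A&G could then mean two things: A&G is added demand, or A&G has displaced direct referral and many requests convert. These carry different messages for commissioners, and the unsplit totals and prevalence cannot tell them apart. Section 10.1.2 plans to release a report of this mapping by month 12 to support local commissioning work.

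**Working it through.** **1. The protocol's own figures (section 4.2.5).** These reproduce and are not in dispute.
- 975,000 / 9 = 108,333 A&G patients a year (stated: 108,000).
- 108,000 / 14,000,000 = 771 per 100,000 (stated: about 800).
- Prevalence half-width 1.96 × √(p(1 − p)/14,000,000) = 4.6 per 100,000 (stated: 5).
- At p = 0.5, the half-width is 0.298% for n = 108,000 and 2.98% for n = 1,080 (stated: 0.3% and 3%).

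**2. Size of the overlap.** Let c be the share of A&G followed by a routine referral. The protocol gives two values to work with: 50%, used in section 4.2.5 for precision, and 61%, the outpatient share in the surgical audit cited in section 1.1.2.
- c = 50%: 0.50 × 108,000 = 54,000 patients a year, or 386 per 100,000, also counted as direct referrals.
- c = 61%: 0.61 × 108,000 = 65,880, or 471 per 100,000.

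**3. Attenuation.** Let D be referrals made without a preceding A&G and A the number of A&G. The recorded series is R = D + cA. With demand and c fixed, let S requests move from direct referral to A&G, so that D becomes D − S and A becomes A + S. The recorded change is −S + cS = −S(1 − c), against a true change of −S.

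| c | Share of the true fall that is recorded |
|---|---|
| 10% | 90% |
| 25% | 75% |
| 50% | 50% |
| 61% | 39% |
| 80% | 20% |
| 100% | 0% |

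This is exact for counts when the conversion falls in the same year. For patient prevalence it also needs the patients who move to have no other routine referral that year.

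**4. Illustration.** The protocol gives no baseline referral rate, starting A&G rate or size of shift. I assume, per 100,000, A = 200 at the start, S = 800, and D between 3,000 and 10,000. For D = 5,000 and c = 50%, R goes from 5,000 + 100 = 5,100 to 4,200 + 500 = 4,700. That is a fall of 400 / 5,100 = 7.8%, against a true 800 / 5,000 = 16.0%.

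| Baseline D | True fall | Recorded, c = 10% | c = 50% | c = 61% | c = 100% |
|---|---|---|---|---|---|
| 3,000 | 26.7% | 23.8% | 12.9% | 10.0% | 0% |
| 5,000 | 16.0% | 14.3% | 7.8% | 6.1% | 0% |
| 10,000 | 8.0% | 7.2% | 4.0% | 3.1% | 0% |

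At D = 5,000 and c = 50%, the A&G-to-direct ratio truly rises from 200 / 5,000 = 0.040 to 1,000 / 4,200 = 0.238. As recorded, it rises from 200 / 5,100 = 0.039 to 1,000 / 4,700 = 0.213. The direction holds and the size shrinks.

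**5. The incidence series.** If the 24-month washout covers either code and runs back from the event, it removes referrals that follow an A&G. If it applies code by code, it does not. If it runs back from the start of the year, where the denominator is set, an A&G and its referral in the same year both still count. Section 4.3 does not say which applies.

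**The case against.** The case on the other side has several parts.

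- **Incidence may already be clean.** On the literal reading in step 5 it is, with a longer look-back than 122 days. This stands, so the point is confined to counts and prevalence, and the washout wording is only an ambiguity.
- **The overlap is measured.** The yearly percentage of A&G followed by a referral, with the yearly A&G count, lets the converted volume be roughly subtracted. This also stands, but only roughly: the percentage is taken among patients with A&G, there are 1.7 million requests for 975,000 people, conversions cross year-ends, and some patients have unrelated referrals. Nothing in section 4.3 ties it back to the first aim.
- **The 50% is a precision assumption**, not a forecast of conversion. Agreed, hence the range of c.
- **Splitting a descriptive series belongs in an analysis plan.** Not here: the protocol itself fixes the measures, and they fit the first aim poorly.

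Two stronger readings are tempting. A reader might infer that the protocol contradicts itself on what direct referral means. It does not. In work package 1a the term denotes a type of event, and the fourth aim openly includes referrals after A&G; when work package 2 means the first pathway, it says so.

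A reader might also infer that the shift could be hidden altogether. The A&G series is unaffected, and at fixed demand the fall in direct referral disappears only as c approaches 100%. A near-flat series at c = 50% needs requests to grow as well. For example, with initial direct referral indexed to 1.00, take A from 0.05 to 0.50 and D from 1.00 to 0.75. R then goes from 1.025 to 1.000, but total requests have risen from 1.05 to 1.25, or 19%. With requests held at 1.05, A reaches 0.30 and R goes from 1.025 to 0.90, so a true fall of 25% reads as about 12%.

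**Conclusion.** The point holds for the annual counts and annual prevalence of routine direct referrals. They include referrals that follow an A&G, so at fixed demand any displacement of direct referral is understated by the conversion share: by half at 50%, and by 61% at the cited audit's figure. The rise in A&G and the direction of the first aim are unaffected.

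This rests on fixed demand and a constant c. The absolute effect cannot be stated, because no baseline referral volume is given. The direct-referral code list is said to be in an appendix that is not shown, so whether any code marks a referral made after A&G could not be checked. For a descriptive study this is a change worth making, not a fault that invalidates the work package.

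**What to change.** In section 4.3, report the counts and prevalence of routine referrals as:
- (a) referrals with no A&G in the preceding 122 days;
- (b) referrals within 122 days after an A&G;
- (c) the total.

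Repeat with 365 days as the sensitivity analysis. For the first aim, present A&G against both (a) and (c); (a) should stand beside the total and not replace it. Show A&G that follows a referral separately, using the 122-day window before the request that is already planned, because the split above does not deal with that direction. State whether the 24-month incidence washout applies to either code and whether it runs back from the event date.

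The cost is one flag per referral, built from dates already linked for the fourth aim, with no new data. The downside is misclassification. Section 4.2.8 accepts that specialty may not be routinely recorded with A&G, so the flag cannot be specialty-specific. Some unrelated referrals will fall into (b), and more of them as A&G grows, which would make (a) fall too far. Showing (c) alongside lets the reader see the range.

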4.2.5 Sample size considerations

The feasibility count of 975,000 individuals gives an estimated mean of 108,000 per annum over the nine years of the study. Assuming an annual denominator population of 14 million (and hence prevalence of A&G of approximately 800/100,000), then per annum 95% confidence limits for the prevalence of A&G will be \pm 5/100,000. For assessing percentage of A&Gs which result in a referral, assuming an estimate of 50%, then per annum 95% confidence limits will be \pm 0.3% overall and \pm 3% for a lowest covariate (e.g., ethnicity group) category prevalence of 1%.

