4.2.7 Definition of the study population

All individuals in the CPRD Aurum database, regardless of age, with an A&G or referral recorded between 01/01/2015 to date of the most recent Aurum build (currently March 2024). For determination of incident A&G, they must have 24 months prior registration in CPRD Aurum or be aged 2 years or under. There is no comparison or control group.

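### WP1a incidence uses one 24-month washout for both routes; read literally, direct-referral incidence falls mechanically as A&G grows

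*Protocol*

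**What the plan says.** Aim 1 of WP1a (Protocol 4.1) is to determine "if use of A&G has increased over time in comparison to direct referrals". Section 4.3 supplies three measures for this: annual counts, annual prevalence and annual incidence, each for A&G and for routine direct referral. Section 4.2.8 says that routine referrals are identified so that prevalence and incidence can be set against those of A&G, so incidence is a planned comparative measure.

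The incidence numerator is "the total number of patients with i) A&G and ii) routine referral codes recorded within each calendar year", restricted to those "who have no recorded A&G or routine referral codes in the previous 24 months". The result is "divided by the total registered population with at least 24 months registration at the start of each calendar year". The numerator clause labels the two series i) and ii). The washout clause does not repeat the labels and contains no word such as 'respectively'. The definition is said to follow earlier work ("Annual incidence will be defined (as in our previous incidence studies"), which is not described further.

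Section 4.2.7 adds a registration rule ("For determination of incident A&G, they must have 24 months prior registration in CPRD Aurum or be aged 2 years or under") but does not say which prior event disqualifies a patient.

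**The concern.** A comparison of two trends needs each series to be free of the level of the other. With a shared washout, a patient whose A&G is followed by a direct referral is removed from the direct-referral numerator, while the denominator still contains that patient. The protocol expects this pathway to be common: aim 4 measures it, and section 4.2.5 plans for it ("For assessing percentage of A&Gs which result in a referral, assuming an estimate of 50" per cent). As A&G grows, so does the group of referrals that cannot be incident. Direct-referral incidence could then drift down although clinicians refer as often as before, and a reader could take this as A&G displacing referral.

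In the other direction, a first A&G in a patient referred to any specialty 20 months earlier does not count as incident A&G, which lowers the level of that series.

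**Working it through.** **1. The plan's own figures.** Section 4.2.5 reproduces: 975,000 / 9 = 108,333 patients a year; divided by 14 million this is 774 per 100,000 (stated as about 800). The 95% limits are 1.96 × √(p(1−p)/14,000,000) = ±4.6 to 4.7 per 100,000 (stated ±5). For a 50% conversion, 1.96 × √(0.25/108,000) = ±0.30% (stated ±0.3%), and with 1,080 patients ±2.98% (stated ±3%). The protocol gives no figure for incidence, for the washout or for the referral rate, so the sizes below rest on assumed ranges.

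**2. What each reading does.** The washout is counted back from the event.

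| Patient history | Literal (combined) washout | Route-specific washout |
|---|---|---|
| First A&G, then first direct referral 3 months later | A&G incident; referral not incident | Both incident |
| Direct referral, then first A&G 20 months later | Referral incident; A&G not incident | Both incident |
| Direct referral only | Referral incident | Referral incident |

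**3. Direct-referral incidence, closed form.** The share of people with an A&G in 24 months at annual level p is 1 − (1 − p)². At p = 0.008 this is 1 − 0.992² = 1.6%. If prior A&G is associated with referral by an assumed odds ratio (OR), the share among referred patients is o/(1 + o), where o = OR × 0.016/(1 − 0.016). This gives 4.6% for OR 3 and 7.5% for OR 5.

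Conversions can be sized separately. They are 0.5 × 800 = 400 per 100,000 a year. Against assumed annual referral prevalences of 5%, 10% and 15%, that is 400/5,000 = 8.0%, 400/10,000 = 4.0% and 400/15,000 = 2.7% of referred patients.

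**4. A&G incidence, closed form.** The share removed for a prior referral is 1 − (1 − r)². For r = 5%, 10% and 15% this is 9.8%, 19.0% and 27.8% under independence, and 24.5%, 41.3% and 53.5% with OR 3.

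**5. Change over time, by simulation.** Assumed, not from the protocol: referral rate 0.05, 0.10 or 0.20 per person-year; A&G rising from 100 to 1,500 per 100,000 over 2015-2023 (midpoint 800, matching 4.2.5); shared gamma frailty with shape 1. The 50% conversion is the protocol's planning value; its timing, within 122 days, uses the window in 4.2.8.

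- Direct-referral numerator lost: about 0.4-1% in 2015. In 2023 about 15%, 9% and 5.5% at rates 0.05, 0.10 and 0.20.
- Total referrals held constant (conversions replace other referrals), rate 0.10: route-specific incidence is 6,940 then 6,882 per 100,000, a change of 6,882/6,940 − 1 = −0.8%. The combined washout gives 6,895 then 6,230, or 6,230/6,895 − 1 = −9.6%. Over the three rates the apparent fall is about 5-16%.
- A&G numerator lost: about 16-19%, 29-30% and 48-53% at the three rates, nearly the same in every year. Without frailty the loss at the lowest rate is nearer the 9.8% of step 4, hence about 10-50% overall.

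**6. Effect on the comparison.** If A&G growth is preserved and direct-referral incidence shows a false fall of 5-16%, the growth in the A&G-to-referral incidence ratio is inflated by 1/0.95 = 1.05 to 1/0.84 = 1.19.

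**7. Measures without a washout.** Annual totals ("We will determine the annual total number of A&G and total number of routine direct referrals from 2015 to 2023") and annual prevalence are defined without reference to prior events, so none of this applies to them.

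**The case against.** The strongest reply is that the sentence can be read distributively: no prior A&G for series i), no prior referral for series ii). The reference to earlier incidence studies may point to that convention. This stands as far as it goes: the mechanical coupling follows from the literal reading only. But nothing in the protocol selects the other reading, and two analysts could code materially different series from the same sentence.

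Second, aim 1 concerns use, and counts and prevalence of both routes are reported alongside incidence. That also stands and limits the point. The trend regressions are described in terms of impact on A&G, so the affected referral series may be used mainly for description.

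Third, a combined washout is a coherent quantity: the route of the first elective request in 24 months. That is true, but it is not labelled so, and it does not compare use of the two routes.

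Three stronger readings are tempting and not supported:

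- **The direct-referral trend changes sign.** This appears in the simulation only when conversions are added on top of a constant referral rate, so that true referrals rise. With the total held constant the true series is flat and the written rule shows a fall.
- **The A&G trend is distorted.** The A&G loss is nearly constant over time. Growth is about 14-fold under either rule, so the level is affected and the relative trend is not.
- **Older patients are affected most, which biases aim 2.** The protocol gives no referral rates by age and the simulation contains no age.

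**Conclusion.** The point holds for the incidence part of the aim 1 comparison. As literally written, the 4.3 washout ties direct-referral incidence to the level of A&G. It produces an apparent decline of about 5-16% over 2015-2023 when total referrals are constant, and a level of A&G incidence about 10-50% below first A&G in 24 months.

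The sizes depend on the assumed referral rates, the A&G growth, the 50% conversion and a washout counted back from the event. At the planned mean A&G level, under independence and before conversions, the direct-referral loss is only 1.6%.

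A reader might infer that aim 1 cannot be answered. The documents do not support that, because the counts and prevalence of both routes are unaffected. The definition should be corrected, but it does not undermine WP1a as a whole.

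**What to change.** In section 4.3, give each series its own washout: incident A&G means no A&G in the previous 24 months; incident routine referral means no routine referral in the previous 24 months. If the combined washout is wanted, report it as a separate measure labelled *first elective request in 24 months, by route*, and do not read it as the aim 1 comparison of use.

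The cost is one sentence in the protocol and one line of code, on the same data extract.
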